2.1.8.2.1 Pharmacokinetic Targets for 10-1074

The 10-1074 target for this study will also be based on the trough after the 3rd dose, C_{84D} . Based on analysis of the PK data from Caskey et al., the expected average concentrations in HIV infected adults with 30mg/kg at steady-state are 150-300 mcg/mL. Single doses of 30 mg/kg and 10 mg/kg in adults exhibited good safety and short-term virologic activity—greater than 1 log HIVRNA reduction. Using a 30 mg/kg dose in young children is expected to be safe and result in 10-1074 concentrations that are about 25% lower than in adults. However, the pediatric concentrations are still expected to exceed those seen in adults following 10mg/kg by several fold. Since 10-1074 has a much shorter half-life than VRC01LS, no “loading” dose is needed to accelerate achievement of steady-state concentrations. Based on safety and tolerability following 30mg/kg in adults, 30mg/kg will be the pediatric dosage used in the current study. Pediatric 10-1074 third dose troughs, C_{84D} , with this dosage are anticipated to be lower at steady-state than expected in adults on 30mg/kg but higher than in adults on 10mg/kg. Therefore, the acceptable target for C_{84D} 10-1074 in this study will be a median that exceeds that expected from 10mg/kg in adults (7.5mcg/mL). The pediatric 30mg/kg dose is expected to result in nearly all of the participants maintaining trough concentrations above the target of 7.5 mcg/mL.

2.1.8.3. Co-administration. Regarding PK considerations for the co-administration of VRC01LS and 10-1074 (in a serial manner), animal data and initial human data suggest no PK concerns when using dual bNAbs. In data recently presented by Cohen et al. at CROI 2018 [50], PK results for the combination of 10-1074 and 3BNC117 were nearly identical to those found when each product was administered alone. This combination closely resembles our combination of 10-1074 with VRC01LS, and provides good assurance that no dosing adjustments will be required when using combination therapy. Step 1 of our study will also closely evaluate for any PK changes with dual bNAb administration in the first 6 participants who receive dual bNAb treatment. Despite the low suspicion that dual bNAb administration will alter PK parameters, the study team and SMC will evaluate for changes from the pre-specified PK targets (as listed above) for both VRC01LS and 10-1074 in these 6 participants to make a decision regarding further enrollment into Step 1 and starting Step 2. Trough PK values will be collected in all subsequent participants and will be stored for later analysis.

2.2. Rationale

2.2.1. Proof of Concept: The EIT cohort provides an ideal low-reservoir pediatric population in which to test whether viral suppression can be maintained for up to 24 weeks with dual bNAb therapy. Children in this cohort will have received at least 96 weeks of ART from very early in life, and will receive 8 weeks of overlapping ART plus VRC01LS/10-1074 prior to stopping ART for up to 24 weeks. Our design is practical in its approach, aiming to demonstrate as a proof-of concept that in a low-reservoir pediatric population dual bNAb therapy alone may be sufficient to maintain viral suppression for 24 weeks. If at least 30% of participants remain virally suppressed after 6 months of dual bNAb treatment following ART cessation, this will be a significant difference from prior cohorts such as the CHER Study where <6% of children treated in the first year of life remained virally suppressed by 6 months off ART in the absence of an intervention [52]. Our study design also allows for detailed study of viral reservoir changes as measured in blood samples during the addition of bNAbs to ART and following transition to bNAb maintenance; it accounts for ethical concerns by offering all participants a potentially effective intervention in a highly controlled manner to maintain viral suppression, while still ensuring interpretable study endpoints; and it is affordable and efficient because of the existing EIT study cohort.

2.2.2. Characterizing the Impact of VRC01LS and 10-1074 on the Infant Virologic Reservoir: We will apply state-of-the art virologic studies to quantify and characterize the viral reservoir in study participants; blood samples. These assays include quantitative digital droplet PCR (ddPCR) measurement of integrated (proviral) HIV-1 DNA, cell-associated HIV-1 RNA, and plasma HIV-1 RNA measured by a highly sensitive single-copy assay [53]. In addition, we will quantify the number of intact proviruses by use of a novel single-genome amplification strategy that combines limiting dilution PCR of near-full-length genomes with next-gen (Illumina) sequencing of the clonal amplicons. This approach will allow us to identify phylogenetic associations between viral sequences longitudinally collected during the proposed study, and is highly informative for characterizing viral sequence evolution and escape mutations in response to bNabs, autologous cellular immune responses or antiretroviral agents. In addition, this assay is more feasible than performing virus outgrowth assays for identifying genome-intact and replication-competent virus, given limitations on blood volume that can be obtained from young children, and helps to track clonal expansion of virally infected cells based on complete sequence identity of viral DNA products generated from discrete cells.

2.2.3. Unique Opportunity for Immunologic Evaluation: A major innovative component of this study is the ability to evaluate immunomodulatory effects of bNAbs on innate and adaptive immune responses in a group of pediatric HIV-1 patients specifically selected to have minimal residual viral reservoirs. So far, investigations of immune effects mediated by bNAbs have been restricted to animal

models or adult HIV-1 patients [36, 37]. While these studies suggested that bNAbs may be able to affect the breadth, magnitude and potency of antiviral humoral and cellular immune responses, immunological effects of bNAbs in the context of a developing immune system in children, specifically in those with an extremely low reservoir of virally infected cells, at present remain entirely unknown. We hypothesize that controlled exposure to low-level viremia during bNAb treatment (in the absence of ART) will support the evolution of highly functional autologous antiviral immune responses that may, in conjunction with direct antiviral effects of the bNAbs, allow for viral control to be maintained for a prolonged time period off conventional ART. In addition, our studies will, for the first time in pediatric patients, allow for detailed profiling of associations between antiviral immune responses and the size and cellular composition of viral reservoir cells in the setting of bNAb treatment.

2.3. Study Hypotheses

2.3.1. Specific Aim 1: VRC01LS and 10-1074 will not be associated with serious adverse events, and median trough concentrations at the doses used will be above established target values of 200 mcg/mL and 7.5 mcg/mL respectively. At least 70% of early-treated low-reservoir children will remain with HIV-1 RNA <400 copies/mL after 24 weeks of receiving VRC01LS and 10-1074 maintenance.

2.3.2. Specific Aim 2: Measurable decline in viral reservoir as measured in blood samples will occur in some children with the addition of dual bNAb therapy to ART. Viral reservoir size prior to receiving ART and prior to receiving VRC01LS and 10-1074, as determined by cell associated HIV-1 DNA and other assays, is inversely correlated to viral rebound kinetics (if rebound occurs on bNAb maintenance). If present, viral rebound will not exceed 1,000 copies/mL prior to re-initiation of ART (and acute retroviral syndrome will not occur). Delayed HIV-1 RNA and DNA suppression patterns in early life will correlate with viral rebound during the ATI. Baseline HIV from most children will be sensitive to VRC01LS and 10-1074, and a decrease in sensitivity will be detectable among children who experience viral rebound.

2.3.3. Specific Aim 3: The breadth of humoral immune responses to HIV-infection will increase following VRC01LS and 10-1074 use. Markers of cellular immune activation may increase on bNAb maintenance. Cell-mediated immune responses to HIV-1 will be preferentially detectable among children with viral rebound.

3. PRIMARY OBJECTIVES

Specific Aim 1: To conduct an interventional clinical trial to determine the safety, pharmacokinetics, dosing and antiviral efficacy of up to 24 weeks of maintenance VRC01LS and 10-1074 immunotherapy in early-treated HIV-1 infected children in Botswana. This uncontrolled, open-label clinical trial will be conducted at two sites in Botswana, using established clinical research infrastructure provided by the Botswana-Harvard Partnership (BHP). The primary endpoints of this study will be the frequency and severity of treatment-associated serious adverse events, and the proportion of children who maintain HIV-1 plasma RNA <400 copies/mL (and <40 copies/mL) 32 weeks after initiating dual bNAb treatment (24 weeks after withdrawal of standard ART). Secondary endpoints will include pharmacokinetic profiles of all children who receive VRC01LS and 10-1074 and growth characteristics of virally suppressed children receiving bNAbs.

Specific Aim 2: To evaluate effects of treatment with VRC01LS and 10-1074 on the size and cellular composition of residual viral reservoirs. Viral reservoirs during treatment with bNAbs will be evaluated in blood samples using a novel single-template, near full-length viral sequencing assay

that provides information on the complete spectrum of HIV-1 DNA copies integrated into host chromosomes. This approach will allow for evaluation of defective vs. intact HIV-1 genomes, antiretroviral drug and CTL escape variants and longitudinal viral sequence evolution in total CD4 T cells as well as in phenotypically-complex subsets of CD4 T cells known to be critical for viral reservoir stabilization. Cell-associated HIV-1 RNA and plasma RNA will be simultaneously analyzed and sequenced. Viral reservoir parameters will be correlated to viral rebound kinetics during ATI, to pharmacokinetic measurements of VRC01LS and 10-1074, and to antiviral immune parameters determined in Specific Aim 3.

Specific Aim 3: To investigate the influence of VRC01LS and 10-1074 treatment on the magnitude and quality of antiviral innate and adaptive immune responses. Data from clinical trials in HIV-1-infected adults show that bNAbs can profoundly influence autologous HIV-1 immune responses. We will use comprehensive phenotypic and functional assays to profile effects of bNAb treatment on biomarkers of immune activation and on innate cellular immune responses, coupled with RNA-Seq-based gene expression studies in selected immune cell subsets. In addition, the evolution of neutralizing antibody breadth and the frequency and functionality of HIV-1-specific T cells will be analyzed, and combined with viral sequencing data (generated in Specific Aim 2) to identify viral immune escape.

4. STUDY DESIGN

PK Step

The first 12 participants in the study will undergo the PK Step, to allow for detailed safety and PK assessment of each bNAb alone. In the PK Step, while continuing ART, participants 1, 3, 5, 7, 9, 11 will receive VRC01LS at Week 0, Week 4, and Week 8 as a single intravenous (IV) dose (30 mg/kg load, then 10mg/kg maintenance); safety and PK measurements will occur at end of infusion, 1 hour post-infusion, 1 day post-infusion, 1 week post-infusion, 2 weeks post-infusion, and 4 weeks post-infusion. Participants 2, 4, 6, 8, 10, 12 will receive 10-1074 at Week 0, Week 4, and Week 8 as a single IV dose (30mg/kg), and safety and PK measurements will also occur at end of infusion, 1 hour post-infusion, 1 day post-infusion, 1 week post-infusion, 2 weeks post-infusion, and 4 weeks post-infusion. In the PK Step, it is anticipated that all 12 participants will be from the EIT Study; however, in the event that 12 participants from EIT are not available at the time the PK Step begins, participants 9-12 may be recruited from other virally suppressed HIV-infected children. These additional, non-EIT children would not be eligible for further study steps after completing the PK Step. In the event that a participant discontinues bNAb during the PK Step, the participant may be replaced to allow for PK data to be obtained from 12 participants total.

SMC Review of Safety and PK Data from PK Step

After all 12 PK Step participants complete the PK Step, safety, PK, and viral suppression data will be reviewed within 8 weeks by the study team, sponsor, and SMC (earlier review by the SMC may be triggered based on pre-specified safety parameters). All PK data from the PK Step will be assessed based on pre-specified PK trough targets; peak values will be assessed, but primary guidance for peak values will be based on toxicity. The study team will determine if median trough concentrations are above the pre-specified targets (see Section 2.1.8), and present this information in a written report to the SMC. In addition, outlier concentrations will be presented and reviewed; the study team expects no more than 2 participants to have trough concentrations below 115 mcg/mL for VRC01LS and no more than 2 participants to have trough concentrations below 5mcg/mL for 10-1074. The SMC and

the study team will review any cases of outlier PK concentrations and make individual recommendations about whether a child with these levels should proceed to Steps 1-3. The SMC will review safety data utilizing pre-defined safety criteria defined in the protocol (see Section 13.8). If safety criteria are met, and if the PK data are in the pre-specified range, approval to begin Step 1 may be granted by the SMC. If the dosing and frequency of bNAbs established in the PK Step is acceptable, it will continue to be used for the first 6 participants in Step 1 (see additional safety review below). If a change in dosing is recommended by experts on the study team (or by the SMC, if it does not accept the team's recommendation), adjustments will occur and IRB and study sponsor approval will be sought regarding required protocol changes prior to starting Step 1. The recommendations by the study team or by the SMC may include early termination of the study, if warranted by the safety/PK data, or a re-design of the study as approved by the study sponsors and regulatory boards.

Step 1 (first 6 participants)

All Step 1-3 participants must be from the EIT Study. After approval, Step 1 will begin for a maximum of 6 participants, all of whom will have participated in the PK Step (3 from each PK Step group), and all of whom will have been >12 weeks from last bNAb dosing. ART is continued throughout Step 1, and all participants receive both 10-1074 and VRC01LS. If dosing recommendations do not change based on the PK Step, a VRC01LS loading dose of 30 mg/kg will be given at the start of Step 1, followed by 10mg/kg dosing at each 4-weekly visit, and 10-1074 dosing will be at 30mg/kg at each 4-weekly visit. At Week 0, Week 4, and Week 8 doses of Step 1, PK testing for both bNAbs will occur prior to infusion, and at Weeks 0 and 4 only at end of infusion, 1 hour post-infusion, 1 day post-infusion, and 1 week post-infusion. HIV-1 RNA will be checked every 4 weeks in Step 1. The first 6 participants in Step 1 will continue in this Step, receiving both oral ART and dual bNAb infusions, until the second study team/SMC review occurs. This review of safety and PK data will occur within 8 weeks of the 6th participant's Week 8 PK sampling.

SMC Review of Safety and PK Data from Step 1 (first 6 participants)

Safety, PK, and viral suppression data for the first 6 Step 1 participants will be reviewed within 8 weeks by the study team, sponsor, and SMC. All PK data will be assessed by the study team based on pre-specified PK trough targets which are the same as those used in the PK Step. The review will confirm that PK targets are met during dual bNAb administration. Safety criteria for the Step 1 data will be reviewed by the SMC, using similar criteria as for the PK Step (see Section 13.8). If safety criteria are met, and if the PK data for both bNAbs are in the pre-specified range, the SMC may approve entry into Step 2 for the first 6 participants and enrollment of additional participants into Step 1. If the PK data are in range and no dosing changes for the bNAbs are required, the dosing will continue to be used for the remainder of the study unless new data emerges requiring additional review. If a change in dosing is recommended by experts on the study team (or by the SMC, if it does not accept the team's recommendation), IRB and study sponsor approval will be sought regarding required protocol changes. The recommendations by the study team or by the SMC may include early termination of the study, if warranted by the safety/PK data, or a re-design of the study as approved by the study sponsors and regulatory boards.

Step 1 (all subsequent participants)

After approval to proceed is obtained by the SMC, additional participants will enroll directly into Step 1 and receive dual bNAbs and ART for 8 weeks. All study visits and follow-up will be the same as for the first 6 Step 1 participants, with the exception of PK testing; only trough PK testing will be required for these participants, beginning at Week 4 of Step 1.

Step 2 (all participants)

Following a successful Step 1 review, Step 2 may begin. Step 2 will begin after a participant has spent at least 8 weeks in Step 1. For the first 6 participants, Step 2 will begin at a scheduled bNAb dosing visit (i.e. 4 weeks from last Step 1 bNAb dosing), and for all subsequent participants it will begin at the 8 Week visit date for Step 1 (which becomes the Week 0 Step 2 visit). Participants with ongoing viral suppression throughout Step 1 will undergo withdrawal of ART and will continue maintenance 10-1074 (30mg/kg) and VRC01LS (10mg/kg) treatment for up to 24 weeks in Step 2. HIV-1 RNA will be checked weekly from Weeks 1-4 in Step 2, and every 2 weeks thereafter. Qualitative HIV DNA will be checked at each visit by DBS. If a participant experiences a single viral rebound ≥ 400 copies/mL in Step 2, ART will be re-started (and VRC01LS and 10-1074 will be discontinued). A single viral rebound is defined as an HIV RNA result ≥ 400 copies/mL at any Step 2 visit, without need for confirmation. If HIV RNA becomes ≥ 400 copies/mL prior to the end of Step 2, all evaluations ordinarily scheduled at “Week 24” will be performed immediately prior to ART re-initiation. If HIV-1 RNA is ≥ 40 copies/mL but <400 copies/mL, or if Qualitative DNA turns from negative to positive, virologic monitoring tests will be repeated *weekly*. Clinical examination will occur at each study visit.

Step 3 (all participants)

All participants will end Step 2 after 24 weeks, and enter Step 3. In Step 3, both 10-1074 and VRC01LS will be discontinued, and ART will be re-started. Follow-up visits in Step 3 will occur at 4, 12, and 24 weeks.

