Additional enrollments **to Step 1** will not occur until approval is granted. If the PK data are in range and no dosing changes for the bNabs are required, the dosing used in Step 1 will continue to be used for the remainder of the study unless new data emerges requiring additional review.

After approval is granted from this second review, the first 6 Step 1 participants will enter Step 2 and discontinue ART, provided they have been in Step 1 for at least 8 weeks; **have completed at least 2 consecutive dual bNAb infusion visits with the third or later dual bNAb infusion scheduled for the Step 2 entry visit;** and have remained with viral suppression <40 copies/mL (Table 5). Additional participants will also enroll in Step 1 at this time (both those who previously participated in the PK Step, and new participants). These participants may also proceed to Step 2 and discontinue ART after 8 weeks in Step 1, if they remain with viral suppression <40 copies/mL. A participant who experiences a confirmed viral rebound \geq 40 copies/mL in Step 1 will discontinue bNabs, complete visit procedures equivalent to those outlined for Step 1 Week 8, and enter Step 3. *(No changes to the remainder of this subsection.)*

6. Section 6.3.1. VRC01LS Dose Calculation Instructions. The first paragraph has been revised to read:

VRC01LS will be dosed at 30mg/kg at the first infusion visit, followed by 10mg/kg maintenance at subsequent infusion visits in the PK Step. Following a recommendation to increase the maintenance dosing of VRC01LS based on review of data from the PK Step, VRC01LS will be dosed at 30mg/kg at the first Step 1 infusion visit, followed by 15mg/kg maintenance at subsequent Step 1 infusion visits. **If a child misses more than 2 doses in Step 1, then VRC01LS will be reinitiated as a loading dose of 30mg/kg IV at the first resumed infusion visit followed by 15mg/kg IV every 4 weeks.**

7. Section 6.4.1. Preparation of VRC01LS IV Solution. This section has been revised to read:

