The purpose of this LOA is to 1) incorporate recommendations of the study team and Safety Monitoring Committee (SMC) following review of data from the PK Step of this trial, specifically a) to increase the maintenance dose of VRC01LS from 10mg/kg to 15 mg/kg every 4 weeks in Step 1 and for the remainder of the study if targets are met, and to provide data from the PK Step supporting this recommendation, b) to maintain the same dose of 10-1074 at 30mg/kg every 4 weeks and to provide data from the PK Step supporting this recommendation, and c) to clarify that the first 6 participants in Step 1 will be selected without consideration of individual results from the PK Step; 2) to extend the time between the first 6 participants completion of Step 1 and the Safety Monitoring Committee (SMC) review of Step 1 data from 8 weeks to 8-10 weeks to allow for adequate time to review; and 3) to update the in-use storage conditions for the prepared

10-1074 in IV bags following the release of the revised Investigator's Brochure version 6.0, dated September 1, 2019.

These changes will affect the following sections of the protocol. Additions to text are shown in **bold**. Deletions are shown in ~~strikethrough~~.

1. Section 1.7. Study Intervention: The following subsections have been revised to read:

Step 1 (first 6 participants)

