Following a successful Step 1 review, Step 2 may begin. Step 2 will begin after a participant has spent at least 8 weeks in Step 1. For the first 6 participants, Step 2 will begin at a scheduled bNAb dosing visit (i.e. 4 weeks from last Step 1 bNAb dosing), and for all subsequent participants it will begin at the 8 Week visit date for Step 1 (which becomes the Week 0 Step 2 visit). Participants with ongoing viral suppression throughout Step 1 will undergo withdrawal of ART and will continue maintenance 10-1074 (30mg/kg) and VRC01LS (**150**mg/kg) treatment for up to 24 weeks in Step 2. HIV-1 RNA will be checked at all visits in Step 2, which occur weekly from Weeks 1-4 in Step 2, and every 2 weeks thereafter. *(No changes to the remainder of this paragraph.)*

2. Section 2.1.8.1. The subheading title is revised as follows: **Initial PK Considerations for VRC01LS in the PK Step.**

The second paragraph has been revised to read:

These PK and safety data for VRC01, coupled with results from adult studies of VRC01LS (VRC 606), allow for dosing estimation for children in the current study. In addition, VRC01LS dosing considerations have been described for children in IMPAACT P1112 [43]. VRC01LS differs by 2 amino acids from VRC01, and is expected to have a similar peak level with a longer half-life and improved concentration at mucosal surfaces. VRC01LS population PK parameters ~~can be~~ were obtained from a PK analysis of study VRC606 **in healthy volunteers** [45] to generate a typical profile for a two-year-old given VRC01LS 30mg/kg loading dose IV followed by two maintenance doses of 10mg/kg (Figure 2).

The first sentence of the third paragraph has been revised to read:

Following administration of the 30mg/kg loading dose, the C_{max} and troughs ~~were~~ are not expected to accumulate much with repeat 10 mg/kg dosing, with the expected steady-state trough concentrations with 10mg/kg IV greater than 400 μ g/mL. (*No changes to the remainder of this paragraph.*)

3. Section 2.1.8.1.1. Pharmacokinetic Targets for VRC01LS: A new subsection heading **2.1.8.1.1.1 VRC01LS target for the PK Step:** has been added to the first paragraph to clarify this subsection pertains to the PK Step only. (*No changes to the remainder of this paragraph.*)

4. A new subsection **2.1.8.1.1.2. Updated PK Considerations for VRC01LS in Step 1:** has been added as follows:

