The VRC01LS concentration 28 days after the second dose (one loading dose of 30mg/kg and one maintenance dose of 15mg/kg), called the Concentration at Day 56 (C56D), will be used to assess adequacy of the dosing regimen. Specifically, if the median C56D of VRC01LS is above 160 mcg/mL (~80% of the original PK Step threshold of 200 mcg/mL accounting for 10-20% accumulation expected with continued dosing) then VRC01LS dosing will be deemed adequate from a PK perspective. If the PK data are above 160 mcg/mL and no dosing changes for VRC01LS are required, the dosing used in Step 1 will continue to be used for the remainder of the study unless new data emerges requiring additional review.

Figure 4. VRC01LS Concentrations in Children in the PK Step compared to Adult Values (Adult simulation data from VRC606)

[figure not shown]
[figure not shown]

Figure 5. Predicted VRC01LS Concentrations using Updated Maintenance Dose of 15mg/kg every 4 weeks

5. Section 2.1.8.2 PK Considerations for 10-1074: A new subsection heading **Initial Dosing Considerations for the PK Step for 10-1074**: has been added to the first paragraph to clarify

this subsection pertains to the PK Step only. (*No changes to the remainder of this subsection.*)

6. Section 2.1.8.2.1. Pharmacokinetic Targets for VRC01LS: A new subsection heading **2.1.8.2.1.1. 10-1074 target for the PK Step:** has been added to the first paragraph to clarify this subsection pertains to the PK Step only. (*No changes to the remainder of this paragraph.*)
7. A new subsection **2.1.8.2.1.2. Updated PK Considerations for 10-1074 in Step 1:** has been added as follows:

Following the PK Step completion and PK data review by the SMC, updated considerations for 10-1074 dosing in Step 1 are as below:

[figure not shown]

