After approval is granted to begin Step 1, 6 of the first 12 PK Step participants will begin dual bNAb treatment per the dosing and follow-up schedule in Table 24. The first 6 Step 1 participants will include 3 participants from each group in the PK Step; these participants may be the first 6 PK Step participants, but this is not required. **In Step 1 dosing for VRC01LS is 30mg/kg load followed by 15mg/kg maintenance, and for 10-1074 30mg/kg.** These Step 1 participants will receive enhanced PK testing for both bNAbs at the Week 0 and Week 4 visits, with pre-infusion testing, testing at end of infusion, 1 hour post-infusion, 1 day post-infusion and 1 week post-infusion (all other PK testing for these participants will be trough pre-dose testing). A review of the safety and PK data for the first 2 dual bNAb doses will occur for these 6 participants. While awaiting this review (see Section 13.8), all 6 participants will remain in Step 1 per follow-up outlined in Table 24, with 4-weekly dual bNAb treatment and ongoing oral ART. Additional enrollments will not occur until approval is granted. **If the PK data are in range and no dosing changes for the bNAbs are required, the dosing used in Step 1 will continue to be used for the remainder of the study unless new data emerges requiring additional review.**

12. Section 6.3.1. VRC01LS Dose Calculation Instructions. The first paragraph has been revised to read: VRC01LS will be dosed at 30mg/kg at the first infusion visit, followed by 10mg/kg maintenance at subsequent infusion visits in the PK Step. Following a recommendation to increase the maintenance dosing of VRC01LS based on review of data from the PK Step, VRC01LS will be dosed at 30mg/kg at the first Step 1 infusion visit, followed by 15mg/kg maintenance at subsequent Step 1 infusion visits.

13. Section 6.4.2. Preparation of 10-1074 IV Solution. This section has been revised to read:

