All participants in Step 2 will continue with monthly dual bNAb maintenance for up to 24 weeks. HIV-1 RNA will be checked at least every 4 weeks while on ART in Step 1, and at every visit in Step 2 (weekly from Weeks 0-4 of Step 2, and every 2 weeks from Week 6-24 of Step 2). Qualitative HIV DNA will be checked at each Step 2 and Step 3 visit by dried blood spot (DBS). Clinical examination will occur at each study visit, except for the 1-day post-infusion PK visits. If participants experience a single viral rebound >400 copies/mL in Step 2, ART will be re-started (and VRC01LS and 10-1074 will be discontinued) without need for confirmation. If HIV RNA becomes ≥ 400 copies/mL in Step 2 prior to the Week 24 visit, all "Week 24" evaluations will be performed immediately prior to ART re-initiation. If HIV-1 RNA is ≥ 40 copies/mL but <400 copies/mL, or if qualitative DNA turns from negative to positive, virologic monitoring tests will be repeated weekly. After 24 weeks in Step 2, or if HIV RNA ≥ 400 copies/mL, participants will discontinue bNAbs, re-start ART and enter Step 3 (Table 3). Participants who enter Step 3 early due to viral rebound will have additional weekly visits until HIV RNA returns to <40 copies/mL. Routine Step 3 study visits will occur at weeks 4, 12, and 24.

6.3.1. VRC01LS Dose Calculation Instructions:

VRC01LS will be dosed at 30mg/kg at the first infusion visit, followed by 10mg/kg maintenance at subsequent infusion visits.

Prior to preparation of the first infusion (enrollment and Step 1 entry visit), a new prescription for VRC01LS will be sent to the pharmacy. The prescription must contain the participant's weight based upon the participant's weight at the most recent visit where weight was measured. Subsequent visit weights (based upon the participant's weight at the most recent visit where weight was measured) must be communicated to the pharmacy in writing prior to the day of the infusion visit. Any changes in weight of more than 10% (between the prior weight and the weight on the day of the infusion visit) will require an updated visit weight communication to the pharmacy in writing so that product can be prepared based on that weight change.

6.3.2. 10-1074 Dose Calculation Instructions:

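### Section 4 still gives VRC01LS as 10 mg/kg in Step 2 after the amendments raised maintenance to 15 mg/kg, and amended Section 6.3.1 no longer states a Step 2 dose

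*Protocol*

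**What the plan says.** **Protocol Section 4, Step 2 (all participants).** Participants who stay suppressed through Step 1 stop ART and "will continue maintenance 10-1074 (30mg/kg) and VRC01LS (10mg/kg) treatment for up to 24 weeks in Step 2".

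**LoA #2, statement of purpose.** Following review of the PK Step, VRC01LS maintenance rises from 10 mg/kg to "15 mg/kg every 4 weeks in Step 1 and for the remainder of the study if targets are met".

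**LoA #2 item 1, Section 1.7, Step 2.** The sentence that matches the Section 4 one was revised. The extracted text shows "VRC01LS (150mg/kg) treatment for up to 24 weeks in Step 2". This is the inserted 5 followed by a struck 0 whose strikethrough was lost in the PDF conversion, so it reads as 15 mg/kg. The same string appears for Step 1 in LoA #2, and LoA #3 prints the Step 1 text cleanly as 15 mg/kg.

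**LoA #2 item 4, Section 2.1.8.1.1.2.** The condition is given as "If the PK data are above 160 mcg/mL and no dosing changes for VRC01LS are required, the dosing used in Step 1 will continue", meaning through to the end of the trial.

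**Section 6.3, as amended by LoA #2 item 11 and re-issued in LoA #3 item 5.** The carry-forward rule, which applies when PK is acceptable, is stated as "no dosing changes for the bNAbs are required, the dosing used in Step 1 will continue to be used for the remainder of", meaning the rest of the trial.

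**Section 6.3.1.** Version 2.0 covered every later visit: "VRC01LS will be dosed at 30mg/kg at the first infusion visit, followed by 10mg/kg maintenance at subsequent infusion visits". As amended, 10 mg/kg is confined to the PK Step, and the Step 1 sentence reads "followed by 15mg/kg maintenance at subsequent Step 1 infusion visits". Step 2 visits are not mentioned.

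**The concern.** Two parts of the operative protocol give different VRC01LS doses for the same infusions. The lower figure is the regimen the study moved away from. LoA #2 reports that, with 10 mg/kg maintenance in the PK Step, the median Day 84 trough was 156.9 mcg/mL against a target of 200 mcg/mL, and that the increase to 15 mg/kg followed SMC review of those data.

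The place matters as well. Step 2 is the only period in which children are off ART, and the primary virologic endpoint is HIV-1 RNA through Week 24 of Step 2. A reader who takes the regimen from the study-design section would attribute the suppression result to the wrong dose. The dose-calculation section does not correct this, because Section 6.4.1 sends the pharmacist to Section 6.3.1, which no longer names Step 2. The SAP does not settle it either: it gives no mg/kg dose for either antibody, and Section 4.1.3 says of Step 2 only that both antibodies were administered every 4 weeks.

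**Working it through.** **Step 1. Trace the Step 2 dose sentence through the amendments.**

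| Text | Section 1.7, Step 2 | Section 4, Step 2 |
|---|---|---|
| Version 2.0 | 10 mg/kg | 10 mg/kg |
| LoA #2 | changed to 15 mg/kg (item 1) | not touched; item 9 revises only Step 1 (first 6 participants) and the Step 1 SMC review, and item 10 moves to Section 5.5 |
| LoA #3 | entry condition added, rest unchanged (item 2) | entry condition added, rest unchanged (item 3) |
| Now in force | 15 mg/kg | 10 mg/kg |

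Removed pages do not explain the gap. The consecutive items on either side of Section 4 are present in both letters. The letters are themselves the amendments in force, so this is a conflict within the amended protocol and not a change log differing from current text.

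**Step 2. Count the places on each side.** Two places name 15 mg/kg for Step 2 or for the rest of the study: the LoA #2 purpose and amended Section 1.7. Two more state 15 mg/kg for Step 1 and carry it forward if PK is acceptable: Section 2.1.8.1.1.2 and Section 6.3. Section 4's own SMC-review text gives no figure but carries Step 1 dosing forward: "the dosing will continue to be used for the remainder of the study unless new data emerges requiring additional review". The same sentence stands in the SMC-review text of Sections 1.7 and 13.8.1. That makes seven places for 15 mg/kg and one for 10 mg/kg, so the intended value is not in doubt, and Section 4 contradicts itself.

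**Step 3. Check the scope of Section 6.3.1.** Before amendment it covered all later infusion visits. After amendment it covers the PK Step (30 then 10 mg/kg) and Step 1 (30 then 15 mg/kg). LoA #3 added a re-loading rule for Step 1 only. No sentence in it gives a VRC01LS dose for Step 2.

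**Step 4. Size the difference.** Inputs: 10 and 15 mg/kg as above. Step 2 infusions fall at Weeks 0, 4, 8, 12, 16, 20 and 24 (protocol Table 3 for Steps 2 and 3; Section 7.7.1). The Week 24 infusion is excluded because ART restarts after it (Section 13), which leaves six that can affect the Week 24 endpoint.

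- Per infusion: 10 / 15 = 0.67, one third lower.
- Over six infusions: 6 × 10 = 60 mg/kg against 6 × 15 = 90 mg/kg, a difference of 30 mg/kg.
- If the Week 0 infusion is treated as a Step 1 visit at 15 mg/kg: 15 + 5 × 10 = 65 mg/kg against 90 mg/kg, and 25 / 90 = 28% lower.
- Illustration for a 12.5 kg child: 12.5 × 10 = 125 mg against 12.5 × 15 = 187.5 mg per infusion; over six, 750 mg against 1,125 mg. The weight is the protocol's simulation weight from the 10-1074 modelling in Section 2.1.8.2. Enrolled children may be heavier, since LoA #1 raised the Step 1 age limit to under 7 years.

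**The case against.** The best case for leaving it alone is that this is clerical residue already overridden. LoA #2 is the later document and states its intent. Section 6.3 is the dosing section and carries Step 1 dosing forward. The Section 4 sentence speaks of continuing maintenance, which by then is 15 mg/kg in Section 4 itself. Section 6.3.1 sits under 6.3 and calls for a new prescription only at enrollment and Step 1 entry, with weight updates afterwards, so the Step 1 dose would ordinarily run on. Step 2 Week 0 must coincide with a Step 1 visit, so 6.3.1 arguably covers that infusion. No analysis, denominator or sample size depends on the sentence. The SAP cites both LoA #2 and LoA #3, and it describes Step 2 in the past tense, so an amendment may come too late to affect dosing.

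Most of this stands as a limit on severity. The practical chance of misdosing is low, the 6.3.1 problem is one of scope and not a conflicting dose, and the cumulative figures describe what the text says, not what was given. It does not make the Section 4 sentence right. A section in force still states a superseded dose for the endpoint period, and an amendment that edited that very paragraph left it there.

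**Conclusion.** The point holds and should be fixed. Section 4 states a VRC01LS dose for Step 2 that is one third below the intended one: 10 against 15 mg/kg per infusion, or 60 against 90 mg/kg over the six infusions before the Week 24 reading. Section 6.3.1 states none.

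This rests on three readings: that the 150 in amended Section 1.7 is 15 with a lost strikethrough; that the Step 1 PK target (median Day 56 trough above 160 mcg/mL) was met, which is the condition for carrying 15 mg/kg forward; and that no other letter or memo, outside the documents available, corrects Section 4. It is an error of documentation in the regimen behind the primary endpoint, not evidence of a dosing error.

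**What to change.** By clarification memo or letter of amendment:

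1. In Section 4, Step 2, change the VRC01LS dose to 15 mg/kg, subject to the Step 1 PK review.
2. In Section 6.3.1, extend the 15 mg/kg sentence to *Step 1 and Step 2* infusion visits.

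If Step 2 is already complete, record both corrections in a note to file instead.

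In either case, use the study-treatment section of the report (SAP Section 5, item 5) to list the VRC01LS mg/kg given at each Step 2 infusion, and flag any departure from 15 mg/kg. The list of protocol deviations already planned as item 3 can carry any that are found.

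The cost is a few words in a memo and one listing in a report section that is already planned. No analysis changes.
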